**Table 8–1: Vital signs abnormality criteria**

Parameter	Age Range	Abnormality Criteria
Pulse Rate (beats/minute)	<6m	<100 >180
	6m - <3y	<90 >150

**Table 8–1: Vital signs abnormality criteria**

Parameter	Age Range	Abnormality Criteria
	3y - <12y	<60 >130
	12y - <17y	≤50 >120
	≥17y	≤50 and a decrease from Baseline of ≥15 >120 and an increase from Baseline of ≥15
Systolic Blood Pressure (mmHg)	<6m	<60 >100
	6m - <3y	<70 >120
	3y - <12y	<80 >140
	12y - <17y	<90 >160
	≥17y	≤90 and a decrease from Baseline of ≥20 >180 and an increase from Baseline of >20
Diastolic Blood Pressure (mmHg)	<6m	<40 >65
	6m - <3y	<45 >75
	3y - <12y	<50 >80
	12y - <17y	≤50 >105
	≥17y	≤50 and a decrease from Baseline of ≥15 >105 and an increase from Baseline of ≥15
Temperature	>1m	>101 °F (38.3 °C)
Body Weight	1m - <17y	<3% or >97% of the normal body weight growth curve ranges a based on gender and the age of subject on date of weight assessment
	≥17y	≥10% change from Baseline (an increase or a decrease)

Abbreviations: m=months, y=years. A month is defined as 28 days; a year is defined as 365.25 days.

a Source: <http://www.cdc.gov/growthcharts/>.

A subject data listing of all vital signs for study subjects with an AE mapped to the PT bradycardia or sinus bradycardia will be presented.

A subject data listing of all vital signs values including body weight, height, BMI, and head circumference for all subjects will be presented. A separate listing including MA vital signs values will also be presented.

#### 8.4.2 Electrocardiograms (ECGs)

Standard 12-lead ECGs (2 interpretable recordings [20 to 30 minutes apart]) will be performed throughout the study, according to the tabular schedules of procedures.

For ECGs, Baseline will be defined as the average of all pre-dose interpretable readings. For all post-Baseline visits, the average of all interpretable readings at the specified visit will be used for summaries.

Observed values of ECG results will be summarized for each visit and Last Visit. Change from Baseline in ECG results will be summarized for all post-Baseline visits, and Last Visit. This will be summarized overall and repeated by weight band using the levels defined in [Section 3.2.10](#).

The number and percentage of subjects with no abnormality, an abnormal but not clinically significant finding, and a clinically significant finding, will be summarized for all visits, and Last Visit. Percentages will be relative to the number of subjects with an ECG assessment at each visit. Subjects are counted at most once at each visit based on the worst observed outcome across all abnormalities reported at that visit.

Summaries of shifts from Baseline to post-Baseline visits, and from Baseline to Last Visit will also be provided based on the categories normal, abnormal, not clinically significant, and abnormal, clinically significant.

A listing of ECG data will be provided for all subjects with other significant TEAEs in the Cardiac and ECG Related Terms category defined in [Appendix 12.2](#). A subject data listing of all ECG parameter values for all subjects will also be presented. Listings will include results from each recording and the average of all recordings.

The number and percentage of subjects with treatment-emergent ECG abnormalities will be presented for each post-Baseline visit and Last Visit. Abnormalities reported at an unscheduled visit will be summarized under the scheduled visit preceding the unscheduled visit (if the abnormality was not present already at the preceding scheduled visit). Treatment-emergent is defined as meeting the criteria at any post-Baseline visit during the Treatment Period (including unscheduled visits) and not meeting the same criteria during Baseline. The age at the time of visit/assessment will be used for determining abnormality criteria (as defined in [Section 3.2.24](#)). All ECG parameter values will be listed for subjects meeting any abnormality criteria.

Abnormality criteria to be used in the determination of ECG abnormalities are defined as follows, where increase and decrease are relative to Baseline values:

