### 3.3 Definition of Baseline values

In general, Baseline will be defined as the last non-missing value collected prior to the first dose of LCM in the previous pediatric studies for efficacy and safety variables, unless otherwise noted for a specific type of data.

The Baseline value for seizure counts (only applicable for subjects from SP0969) will be taken from the subject diary completed during the 8-week Baseline Period before receiving LCM in study SP0969.

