## 8.4 Vital signs, physical findings, and other observations related to safety

### 8.4.1 Vital signs, body weight, height, BMI, and head circumference

Vital signs (systolic BP [SBP], diastolic BP [DBP], and pulse rate) will be assessed after at least 3 minutes at rest in a supine position throughout the study, according to the tabular schedules of procedures. Body weight, height, and head circumference will also be assessed throughout the study, according to the tabular schedules of procedures.

Assessment of orthostatic changes (only in ambulatory subjects) will also be performed as follows: after the 3 minute measurement in supine position, the subject is asked to stand up, and SBP, DBP and pulse rate are taken approximately 1 minute and approximately 3 minutes after the subject stands up, as feasible.

Observed values of SBP, DBP, pulse rate, body weight, height, BMI, and head circumference will be summarized for each visit and Last Visit. Change from Baseline for SBP, DBP, pulse rate, body weight, height, BMI, and head circumference will be summarized for all post-Baseline visits, and Last Visit.

Orthostatic changes of SBP, DBP, and pulse rate will be summarized for each visit and Last Visit.

Markedly abnormal (MA) values are defined as those MA values during the defined Treatment Period at scheduled or unscheduled visits which occur on or after the first EP0034 LCM administration through to the end of the study. The age at the time of assessment will be used for determining MA (as defined in Section 3.2.24).

The number and percentage of subjects with a MA value, MA low value, and MA high value, at each post-Baseline visit and Last Visit, for which SBP, DBP, pulse rate, and body weight are scheduled to be assessed, and Last Visit, will be presented. Percentages will be relative to the number of subjects with a value at each time point.

The abnormal vital sign criteria are defined as follows:

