**Table 8–2: ECG abnormality criteria**

Parameter	Age Range	Abnormality Criteria
QT interval (ms)	1m - <12y	≥500

Parameter	Age Range	Abnormality Criteria
	≥12y	≥500 or ≥60ms increase from Baseline
QTc(F) (ms)	<6m	>490, or >15% increase from Baseline
	6m - <3y	>440, or >15% increase from Baseline
	3y - <12y	>440, or >15% increase from Baseline
	≥12y - <17y	>440, or >15% increase from Baseline
	≥17y	≥500 or ≥60ms increase from Baseline
QTc(B) (ms)	<6m	>490, or >15% increase from Baseline
	6m - <3y	>450, or >15% increase from Baseline
	3y - <12y	>450, or >15% increase from Baseline
	≥12y - <17y	>450, or >15% increase from Baseline
	≥17y	≥500 or ≥60ms increase from Baseline
PR interval (ms)	<6m	>150, or ≥25% increase from Baseline
	6m - <3y	>170, or ≥25% increase from Baseline
	3y - <12y	>180, or ≥25% increase from Baseline
	≥12y - <17y	>200, or ≥25% increase from Baseline
	≥17y	Treatment-emergent value >200, >220, >250
QRS interval (ms)	<6m	>90, or ≥25% increase from Baseline
	6m - <3y	>90, or ≥25% increase from Baseline
	3y - <12y	>100, or ≥25% increase from Baseline
	≥12y - <17y	≥110, or ≥25% increase from Baseline
	≥17y	Treatment-emergent value >100, >120, >140
Heart rate (bpm)	<6m	<100, >180
	6m - <3y	<90, >150
	3y - <12y	<60, >130
	≥12y	<50, >120

Abbreviations: bpm=beats per minute; m=months; ms=milliseconds; QTc=corrected QT interval; y=years. A month is defined as 28 days; a year is defined as 365.25 days.

A subject data listing will be provided that identifies subjects with a clinically significant finding after the first dose of LCM for each type of ECG abnormality.

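### From age 17 the body-weight criterion becomes any 10% change from a Baseline taken before 17, so ordinary growth alone can be counted as markedly abnormal; the ECG rule at the same age needs one clarifying sentence

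*SAP*

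**What the plan says.** **Weight.** SAP 8.4.1 states: "The age at the time of assessment will be used for determining MA (as defined in Section 3.2.24"). It counts any MA value from the first EP0034 dose to the end of the study and, unlike the laboratory rule in SAP 8.3, does not require the value to have been normal at Baseline. MA, MA-low and MA-high are tabulated at each post-Baseline visit and at Last Visit. In Table 8-1, weight from 1 month to under 17 years is MA if it lies below the 3% or above the 97% limit of the growth curve for sex and age on the day. At 17 and over the criterion is "≥10% change from Baseline (an increase or a decrease").

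SAP 3.3 sets the reference point: "Baseline will be defined as the last non-missing value collected prior to the first dose of LCM in the previous pediatric studies". Protocol sections 1 and 5.4 give the SP0969 age range as 4 to under 17 years.

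**ECG.** SAP 8.4.2 calls an abnormality treatment-emergent if the criteria are met after Baseline while "not meeting the same criteria during Baseline". The next sentence reads "The age at the time of visit/assessment will be used for determining abnormality criteria". In Table 8-2 the QRS limit at 12 to under 17 years is "≥110, or ≥25% increase from Baseline"; at 17 and over it is "Treatment-emergent value >100, >120, >140".

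**The concern.** The weight criterion changes in kind at a birthday. Up to 17 it asks whether the weight is unusual for a child of that age, and growth is built in. From 17 it asks whether the weight has moved 10% from a fixed earlier value, and growth is not built in. The second rule suits adults whose weight should be stable. Here it is applied to adolescents whose reference weight was taken earlier in adolescence.

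The table is read as a possible drug effect in a study whose primary objective is long-term safety. Under SAP 3.1 the default age split is by age at entry, 1 month to under 4 years and 4 to under 18 years. Flags from the 17-and-over row would therefore be pooled with those of much younger children, and the table would not show where they came from.

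The ECG question is narrower. The QRS limit falls from 110 to just above 100 ms at 17, so the handling of an unchanged value between those limits depends on which age band is applied to the Baseline reading.

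**Working it through.** The plan states no figure on this point to reproduce.

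**Inputs from the documents**
- Last Treatment Period visit: Week 96 (Protocol 5.1).
- SP0969 age range: 4 to under 17 years.
- Weight and QRS rows of Tables 8-1 and 8-2, and Baseline from SAP 3.3.

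**Assumed, because the documents do not give them**
- Time from Baseline to EP0034 entry: 0, 3 or 6 months.
- Growth rates: ranges shown below.

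**Who can reach the 17-and-over row.** 96 × 7 / 365.25 = 1.84 years. 17 − 1.84 = 15.16, so a subject aged about 15.2 or more at entry can be assessed at 17 by Week 96.

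**Growth that meets the rule.** Annual rate = 1.10^(1/t) − 1, where t is the time in years from Baseline to the assessment.
- t = 1.84: 5.3% per year
- t = 2.09 (3 months added): 4.7%
- t = 2.34 (6 months added): 4.2%

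In kilograms, the rate is 0.10 × Baseline weight / t:

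| Baseline weight | Gain needed | kg/year, t = 1.84 | kg/year, t = 2.34 |
|---|---|---|---|
| 40 kg | 4 kg | 2.2 | 1.7 |
| 50 kg | 5 kg | 2.7 | 2.1 |
| 60 kg | 6 kg | 3.3 | 2.6 |
| 70 kg | 7 kg | 3.8 | 3.0 |

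Conversely, at assumed growth of 3%, 5%, 6% or 8% per year, the change over 1.84 years is 1.03^1.84 − 1 = 5.6%, then 9.4%, 11.3% and 15.2%. The first two stay below the limit and the last two cross it. For a 50 kg subject, an assumed 1 to 5 kg/year gives 3.7% to 18.4%.

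**QRS held constant.** The QRS rows were applied to an unchanged value from 70 to 149.5 ms in 0.5 ms steps. Half-millisecond values can occur because "the average of all interpretable readings at the specified visit will be used for summaries".

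| Age at Baseline and visit | Baseline judged by age at Baseline | Baseline judged by age at the visit |
|---|---|---|
| 16 and 17.1 | flags 100.5 to 109.5 ms | none |
| 11 and 12.5 | none | none |
| 2.5 and 3.5 | none | none |
| 15.5 and 16.9 (same band) | none | none |

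In whole milliseconds the affected range is 101 to 109. Among the QRS crossings tested, only the one at 17 depends on the reading.

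**The case against.** **Weight.** The strongest reply is that the table does not stand alone. MA-low and MA-high are shown separately, observed weight and change from Baseline are summarised by visit, and every value is listed. A careful reader could therefore trace an MA-high flag to growth. The study is descriptive, and weight is not one of the primary safety variables. All of this is correct and limits the harm, but it does not justify a count whose meaning changes on a birthday.

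A reader might also infer that growth produces new or treatment-emergent weight abnormalities. The documents do not support that wording: weight is reported as MA, with no emergence condition.

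**ECG.** A reader might infer that every unchanged QRS of 101 to 109 ms becomes treatment-emergent at 17. The text does not support this. The criterion met at 17 is above 100 ms, and a Baseline of 105 ms meets that same criterion, so the exclusion "not meeting the same criteria during Baseline" removes it. The opening words of "Treatment-emergent value >100, >120, >140" point the same way. What remains is an ambiguity. The sentence on age at visit can be programmed so that the Baseline visit takes the limit for its own age, and the two programs would give different tables.

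Nor does turning 17 only create events. In Table 8-2 the QTcF absolute limit loosens from above 440 to 500 ms or more, and QTcB from above 450 to 500 ms or more. In Table 8-1 the pulse and blood-pressure rows gain a change-from-Baseline condition.

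**Conclusion.** The weight point holds. From 17, growth since a younger Baseline can by itself meet the MA rule, including in a subject whose percentile has not moved. The threshold is about 5.3% per year over 1.84 years, or 4.2% to 4.7% if 3 to 6 months passed between Baseline and entry. Whether typical subjects exceed it depends on growth rates that the documents do not give, and half of the assumed rates above do not reach it. The number affected cannot be derived; it is confined to subjects who are assessed at 17 or over.

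The ECG point is a request for clarification. On the literal reading there is no error. The SAP should settle the reading because the alternative would report unchanged QRS values as treatment-emergent. The same clarification covers limits that fall with age elsewhere in Table 8-2, such as QTcF from above 490 to above 440 ms at 6 months, and the upper heart-rate limit from 150 to 130 bpm at 3 years.

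**What to change.** **Table 8-1, body weight.** For subjects whose Baseline weight was taken before age 17, continue the growth-curve criterion at 17 and over in place of the 10% increase, and retain the 10% decrease from Baseline.

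**SAP 8.4.2.** Add: *For treatment emergence, the Baseline value is judged by the limits of the age band that applies at the post-Baseline assessment.*

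**Cost.** This takes two short edits and a small programming change.
- A gain of 10% or more that stays within the growth-curve limits is no longer flagged at 17 and over. Because essentially all Baselines in that row are before 17, this removes the increase rule from nearly the whole row. The same limitation already applies below 17, and the gain still appears in the change-from-Baseline summaries and the listings.
- A subject below the low growth-curve limit would continue to be flagged after 17, which the current row does not do.
- The retained decrease rule still runs from the fixed Baseline. After growth from 50 to 55 kg it fires at 45 kg, a loss of 10/55 = 18% of current weight.
- The sponsor should confirm that the growth reference cited in Table 8-1 covers the ages reached on study.
- Under the ECG sentence, a QTc or heart rate that stays flat while its limit falls with age is not treatment-emergent. The value is still listed.

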**Table 8–2: ECG abnormality criteria**

Parameter	Age Range	Abnormality Criteria
QT interval (ms)	1m - <12y	≥500

Parameter	Age Range	Abnormality Criteria
	≥12y	≥500 or ≥60ms increase from Baseline
QTc(F) (ms)	<6m	>490, or >15% increase from Baseline
	6m - <3y	>440, or >15% increase from Baseline
	3y - <12y	>440, or >15% increase from Baseline
	≥12y - <17y	>440, or >15% increase from Baseline
	≥17y	≥500 or ≥60ms increase from Baseline
QTc(B) (ms)	<6m	>490, or >15% increase from Baseline
	6m - <3y	>450, or >15% increase from Baseline
	3y - <12y	>450, or >15% increase from Baseline
	≥12y - <17y	>450, or >15% increase from Baseline
	≥17y	≥500 or ≥60ms increase from Baseline
PR interval (ms)	<6m	>150, or ≥25% increase from Baseline
	6m - <3y	>170, or ≥25% increase from Baseline
	3y - <12y	>180, or ≥25% increase from Baseline
	≥12y - <17y	>200, or ≥25% increase from Baseline
	≥17y	Treatment-emergent value >200, >220, >250
QRS interval (ms)	<6m	>90, or ≥25% increase from Baseline
	6m - <3y	>90, or ≥25% increase from Baseline
	3y - <12y	>100, or ≥25% increase from Baseline
	≥12y - <17y	≥110, or ≥25% increase from Baseline
	≥17y	Treatment-emergent value >100, >120, >140
Heart rate (bpm)	<6m	<100, >180
	6m - <3y	<90, >150
	3y - <12y	<60, >130
	≥12y	<50, >120

Abbreviations: bpm=beats per minute; m=months; ms=milliseconds; QTc=corrected QT interval; y=years. A month is defined as 28 days; a year is defined as 365.25 days.

A subject data listing will be provided that identifies subjects with a clinically significant finding after the first dose of LCM for each type of ECG abnormality.

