6.3 Withdrawal criteria

Subjects are free to withdraw or the subject's legal representatives are free to withdraw the subject from the study at any time, without prejudice to their continued care.

Participation in this study **must** be discontinued for any of the following reasons:

1. Subject experiences intolerable AEs, including clinically relevant abnormal laboratory findings that, in the opinion of the investigator, preclude further participation in the study.
2. The sponsor or a regulatory agency requests withdrawal of the subject.
3. Subject has a QTc interval ≥ 500 ms that is confirmed by a cardiologist over read on any ECG.
4. Subject develops a second-degree atrioventricular (AV) block while awake or develops a third-degree AV block.
5. For subjects ≥ 6 years of age, subject has actual suicidal ideation since last visit as indicated by a positive response ("Yes") to either Question 4 or Question 5 of the C-SSRS. The subject should be referred immediately to a Mental Healthcare Professional and must be withdrawn from the study.
6. Subject is unwilling or unable to continue or legal representative is unwilling or unable to allow the subject to continue in the study.
7. Investigator decides that withdrawal from further participation would be in the subject's best interest.
9. Female subject who achieves menarche during the study and does not practice contraception as provided in Exclusion Criteria 5 unless sexually abstinent.

10. Subject becomes pregnant, as evidenced by a positive pregnancy test.

Participation in this study **may** be discontinued for any of the following reasons:

1. Any clinically relevant change in medical or psychiatric condition (if, in the opinion of the investigator, the condition warrants discontinuation from the study).
2. Subject requires a medication that is not permitted by the protocol (see Section 7.8.1).
3. Subject and/or legal representative is noncompliant with study procedures or medication, in the opinion of the investigator.

Subjects discontinuing LCM for any reason should taper off medication as described in Section 7.2.2. Whenever possible, these cases should be discussed with the Medical Monitor prior to withdrawing the subject from the study.

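### Under age 17 no SAP table counts QTc ≥500 ms, the protocol's discontinuation threshold, and the treatment-emergent rule can omit a child whose Baseline QTc already exceeded the paediatric limit

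*SAP*

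**What the plan says.** Protocol Section 6.3 (third mandatory criterion) requires discontinuation for a QTc of at least 500 "ms that is confirmed by a cardiologist over read on any ECG". It sets no age limit and names no correction formula.

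SAP Table 8–2, read by age at assessment, gives these QTc criteria:

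- QTcF, 6 months to under 17 years: ">440, or >15% increase from Baseline"
- QTcB, 6 months to under 17 years: ">450, or >15% increase from Baseline"
- QTcF and QTcB, under 6 months: ">490, or >15% increase from Baseline"
- QTcF and QTcB, 17 years and over: "≥500 or ≥60ms increase from Baseline"

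Below age 17, 500 ms appears only in the uncorrected QT rows (from 1 month, with a 60-ms rise as an alternative from age 12).

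SAP Section 8.4.2 defines a treatment-emergent ECG abnormality as one that meets the criterion at a post-Baseline visit in the Treatment Period, unscheduled visits included, "and not meeting the same criteria during Baseline". Baseline is the mean of the pre-dose interpretable readings. Post-Baseline summaries use the mean of the visit's readings.

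**The concern.** Long-term safety is the primary objective, and SAP Appendix 12.2 already singles out QT prolongation as a significant event. The parent studies enrolled children from 1 month to under 4 years and from 4 to under 17 years, so most ECGs in this study will be judged on the rows for ages under 17. On those rows the protocol's own stopping value is not a criterion.

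There are two consequences. First, a flagged child at 505 ms looks the same in the table as one at 441 ms. Second, a child who was above the paediatric limit before lacosamide may reach the stopping value and not count as treatment-emergent on that QTc row. The report could then contain no number of children at the limit the protocol treats as mandatory for discontinuation, and the nearest table could understate it.

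**Working it through.** The plan states no figure to reproduce, so the check applies its rules to possible values.

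**Inputs.** B is Baseline QTc, T is on-treatment QTc and L is the absolute limit in Table 8–2 (440, 450 or 490 ms). The rise limb fires when T > 1.15 × B. The stopping value is 500 ms (Protocol Section 6.3).

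**Baseline at or below the limit (B ≤ L).** Since 500 exceeds 440, 450 and 490, every T ≥ 500 meets the absolute limb, and neither limb was met at Baseline. The child is always flagged.

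**Baseline above the limit (L < B < 500).** The absolute limb was already met at Baseline, so only the rise limb could flag the child. At T = 500 it cannot, because the rise is too small:

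| Row | L (ms) | Whole-number Baselines affected | Largest rise to 500 | Rise limb at the lowest of these Baselines |
|---|---|---|---|---|
| QTcF, 6 months to <17 years | 440 | 441–499 (59) | 500/441 − 1 = 13.4% | T > 1.15 × 441 = 507.15 |
| QTcB, 6 months to <17 years | 450 | 451–499 (49) | 500/451 − 1 = 10.9% | T > 1.15 × 451 = 518.65 |
| Either, <6 months | 490 | 491–499 (9) | 500/491 − 1 = 1.8% | T > 1.15 × 491 = 564.65 |

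All three largest rises are below 15%, so T = 500 is unflagged at every one of these Baselines. The silent band widens as Baseline rises. For QTcF it ends at 1.15 × 445 = 511.75, 1.15 × 450 = 517.5 and 1.15 × 460 = 529 ms. For QTcB it ends at 1.15 × 455 = 523.25 ms. For example, QTcF 445 to 505 (+13.5%) is not flagged, whereas 445 to 520 (+16.9%) is.

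**What counts as the same criterion.** The above judges the two limbs separately. If the whole row joined by 'or' is one criterion, a child with B > L met it at Baseline and no later value can count. The SAP does not say which reading applies.

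**Whether another row catches the child.** Take QTcF 445 to 500 with heart rate constant, QT = QTcF × RR^(1/3) and QTcB = QT/RR^(1/2).

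- At 60 bpm (RR = 1) all three measures coincide. QT reaches 500 and QTcB goes from 445 to 500, crossing 450. Both rows flag the child.
- At 80 bpm (RR = 0.75) QT goes from 404 to 454, below 500 and a rise of only 50 ms. QTcB goes from 467 to 525, already above 450 at Baseline and up 12.4%. No QT or QTc row flags the child.

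**A stand-alone criterion.** If T ≥ 500 is its own criterion, any child with B < 500 and T ≥ 500 is treatment-emergent. Adding ≥500 inside the existing 'or' row would not achieve this under the whole-row reading, because B > L already meets the row.

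**Averaging.** As an illustration, two readings of 490 and 505 ms average (490 + 505)/2 = 497.5 ms. A row based on the visit mean would miss a recording at the limit.

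**The case against.** A reader might infer that the missing 500-ms row hides any child under 17 who reaches the stopping value. The documents do not support that: the paediatric limits are lower than 500 ms, so every child who starts at or below them is flagged. The omission needs a Baseline already above the limit.

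Nor can that group be sized, and it may be empty. No Baseline QTc distribution is given, and the parent studies' ECG entry limits and withdrawal criteria are not in these documents. The eligibility criteria of this study set no numeric QTc limit, so they do not exclude such Baselines, but Exclusion Criterion 2 bars anyone meeting a mandatory withdrawal criterion of the parent study.

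A reader might also infer that these children would appear only in listings. That is too strong. SAP Section 8.4.2 plans summaries of observed values and changes by visit, and descriptive statistics include the maximum. It also plans tables and shifts by clinical significance. A discontinued child enters the disposition table, and the adverse event tables if an event is reported. None of these, however, gives a count at a QTc threshold: clinical significance is a judgment, and the disposition and adverse event tables depend on the recorded reason or coded term.

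It can be added that nothing obliges Table 8–2 to reproduce withdrawal criteria, and that some subjects turn 17 on study and move to the 500-ms row. Both are true. Yet SAP Section 8.3 does tabulate subjects meeting the protocol's liver injury criteria, and Table 8–2 already gives several cut-offs for PR and QRS from age 17, so a count at a protocol limit fits the plan's own practice.

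**Conclusion.** The point holds as a worthwhile improvement to a safety table. For subjects under 17, no planned table counts QTc ≥500 ms, and the treatment-emergent rule can drop a child with Baseline QTcF above 440 ms, QTcB above 450 ms, or either above 490 ms under 6 months. On that row the child is dropped if the rise is no more than 15%, or whatever the rise if the whole row is one criterion. At exactly 500 ms this covers every Baseline between the limit and 500 ms. The QT row or the other QTc row catches some cases, depending on heart rate.

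The logic follows from the text alone, assuming only that the table is built row by row from Table 8–2. How many children are affected is unknown. No recorded value is lost; what is missing is the count.

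**What to change.** In SAP Section 8.4.2, add a stand-alone number and percentage of subjects of any age with QTcF ≥500 ms and, separately, with QTcB ≥500 ms. Both are needed because the protocol names no correction formula.

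- Keep these rows apart from the existing criteria, not joined to them by 'or', and judge treatment-emergence against 500 ms alone.
- Base them on any single on-treatment recording, including unscheduled ECGs, and not on the visit mean, because the protocol rule acts on any ECG.
- Note that the count is of recorded values; the cardiologist's confirmation is a separate step.
- State whether the phrase "not meeting the same criteria during Baseline" refers to each limb or to the whole row.

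The cost is two table rows and a few lines of SAP text, with no new data. The threshold is the protocol's own, and no clinical rule is proposed.
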